6.5.2 Extrusion of the Punctal Plug after the Baseline Visit

A study subject that has noticed a plug has been extruded or lost during the follow-up period should immediately contact the Investigator and/or his/her staff and return to the Investigator's office as soon as possible. The Investigator will terminate the study subject from the study and will NOT be replaced.

6.6 Study Plug Accountability and Storage Procedures

The Investigator is responsible for maintaining the study treatment (punctal plug) accountability log, which will contain inventory records acknowledging the receipt and dispensing of all study plugs. The study center will keep a complete accounting of all used, unused, damaged, extruded and lost study plugs. All lost/extruded study plugs must be recorded into the accountability log and on the CRFs of the study subject who lost/extruded his/her study plug, noting the suspected date the study plug was lost/extruded.

All used and unused study plugs must be accounted for and kept in the designated secure area at the study center until the Sponsor provides instructions for the return of all study materials. Final accountability for study plugs will be verified by the Sponsor and/or his/her representatives and considered complete when the study plugs are no longer actively used and all study plugs (used, unused, extruded, lost) have been accounted for and returned to the Sponsor.

7 STUDY PROCEDURES AND SCHEDULE

Data will be captured and compiled using procedures developed by representatives of Mati Therapeutics Inc. All requested study data must be recorded clearly on study NCR CRFs and other study forms, as required. An explanation must be provided for all missing data. Only the Investigator or his/her staff members who are identified on the Study Personnel Delegation of Authority form may enter or correct data on a CRF. Incomplete or inconsistent data on the CRFs will result in data queries that will require resolution by the Investigator.

7.1 Protocol Amendments

Modification of the protocol is prohibited without prior written agreement in the form of a protocol amendment. All amendments will be created by the Sponsor and must be approved by the IRB

prior to implementation except when required to mitigate immediate safety risks or when the changes involve only logistical or administrative revisions.

7.2 Study Procedures/Evaluations

7.2.1 Study Specific Procedures

Procedures that are required during the course of the study include:

- a. Informed consent and HIPAA authorization: The Investigator and or qualified staff will review and answer any questions a potential study subject may have regarding the study, the consent or HIPAA authorization forms. Prior to the initiation of any study specific activities, the subject must sign both documents
- b. Record subject's demographic data and medical history for the previous 7 days
- c. Record any subject reports of any ocular signs or symptoms they may be experiencing
- d. Slit-Lamp Examination: Slit-lamp examination will include assessment of the lid, conjunctiva and cornea as normal or abnormal. If a finding is indicated as abnormal, the investigator will indicate if the finding is clinically significant. If the finding is considered clinical significant, the investigator will describe the finding in the section provided on the Case Report form
- e. Evaluation of the subject tear lake: Using a slit lamp micrometer, the micrometer will be oriented vertically and centered on the lower lid margin at the middle of the lower lid. The tear lake will be measured using the slit lamp micrometer from the lid margin to the superior border of the lower tear lake and measured to 0.1 mm.
- f. Punctum size evaluation prior to dilation: Using the Coroneo punctum dilator, the narrow end of the dilator has calibrated rings that correspond to punctum diameters of 0.5, 0.6 and 0.7 mm. The rings on the wide end of the dilator correspond to punctum diameters of 0.8, 0.9 and 1.0 mm. Prior to measuring the punctum diameter, the eye should be anesthetized (see [Section 6.2](#) of the protocol for details) with a topical anesthetic. The narrow end of the dilator is then introduced vertically into the punctum and advanced until the punctum starts to invert. The diameter is recorded as the nearest ring to the edge of the punctum when inversion begins. If the punctum diameter is larger than 0.7 mm, the narrow end of the dilator is removed, and the wider end inserted and advanced in the same way. Again, the diameter is recorded as the nearest ring when inversion begins.
- g. Insertion of a study punctal plug (see [Section 6.2](#) of the protocol for details)
- h. Removal of a study punctal plug (see [Section 6.6](#) of the protocol for details)
- i. Adverse Device Event reporting, see [Section 8.5](#) of the protocol for details: To optimize consistency of ADE reporting across centers, the study subject will be asked a standard question to elicit any ADEs. At each study visit or telephone evaluation of the study subject, study personnel will ask the following question:

“Have you had any problems since your last visit?”

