2.3 Potential Risks and Benefits

The risks of the NDE L68 StableFit® punctal plug is not fully known but are expected to be similar to those observed for commercial punctal plugs, which are considered to be low. Some risks associated with punctal plug use are discomfort, epiphora, loss of plug, inflammation, and subconjunctival hemorrhage. Less common, but serious, side effects are pyogenic granuloma, damage to the muscle at the opening of the punctum, canaliculitis, or migration of the plug into the canalicula, requiring irrigation or surgery. In controlled clinical trials of the Mati punctal plugs, rates of serious adverse device events have been less than 1 percent ([Fayet 1990](#), [Balaram 2001](#), [Kim 2005](#)).

There are no treatment benefits to study participants. Study subjects will receive regular eye exams.

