4.2.3 Safety Endpoints

Safety assessments will include any clinically significant slit-lamp biomicroscopy findings, any extrusions of a punctal plug, and incidence and severity of any reported ADEs after punctal plug insertion.

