7.3 Study Visit Schedule

7.3.1 Visit 1: Day 0 - Screening (Prior to punctal plug insertion)

A potential study subject qualifications will be assessed according to the inclusion/exclusion criteria listed in the protocol (see Sections 5.2 and 5.3). Prior to undergoing any study-specific procedures, both the study Informed Consent and Authorization for Use/Disclosure of Health Information forms (HIPAA authorization) must be signed by a potential subject who has agreed to participate in the study. During this visit, the following information will be collected/evaluated and recorded in the appropriate sections of the study case report forms of a subject, prior to the sizing and dilation of the lower punctum for the planned study eye.

- a. Obtain informed consent and HIPAA authorization release
- b. Record the subject's demographic data and prior 7 days medical history
- c. Verify a subject has not used any ocular drops within the last hour prior to their baseline visit
- d. Record any subject reports of ocular signs or symptoms they are currently experiencing
- e. Slit-lamp examination of the planned study eye

7.3.2 Visit 1:Baseline - Day 0 (Insertion of a punctal plug - refer to Section 6.2 for details regarding the insertion of the NDE punctal plug)

After the screening examination, a qualified study subject will be sequentially assigned an ID number. In addition, the ID number and the study subject initials will be recorded on study case report forms, in lieu of recording his/her name, in order to maintain subject confidentiality.

Note: The investigator has the option of inserting the plug in either the left or right eye of the subject. However, if the investigator is unable to insert the plug in the first eye chosen, the investigator can insert the plug in the fellow eye as long as the fellow eye meets all study inclusion/exclusion criteria.

- f. Tear lake evaluation of the planned study eye prior to the sizing and dilation of the lower punctum
- g. Size evaluation of the punctum of the planned study eye prior to the dilation of the lower punctum
- h. After dilation, the study punctal plug is inserted in to the lower punctum of study eye, inspect the punctal plug using the slit-lamp, the position of a study punctal plug may be adjusted with forceps.
- i. Record any reported adverse device event(s)

j. After the study plug has been inserted in the lower puncta, the investigator will assess the insertion characteristics of the plug.

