7.3.3 Visit 2: Follow-Up (Day 7 + 1 post plug insertion)

At this visit the following will be performed and recorded:

- a. Verify a subject has not used any ocular drops, in their study eye, within the last hour prior to their scheduled visit
- b. Slit-lamp examination of the study eye
- c. Inspection of the punctal plug via the slit lamp
- d. Tear lake evaluation of the study eye
- e. Recording of any reported adverse device event(s)

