7.3.4 Visit 3: Follow-Up (Day 28 + 4 post plug insertion)

At this visit the following will be performed and recorded:

- a. Verify a subject has not used any ocular drops, in their study eye, within the last hour prior to their scheduled visit
- b. Investigator evaluation of subject's acceptability of the punctal plug, prior to the removal of the punctal plug
- c. Slit-lamp examination, prior to the removal of the punctal plug
- d. Inspection of the punctal plug via the slit lamp, prior to removal of the plug
- e. Tear lake evaluation of the eye prior the removal of the punctal plug
- f. Removal of the punctal plug (refer to [Section 6.6](#) for details regarding the removal of a punctal plug)
- g. Recording of any reported adverse device event
- h. After removal of the study subject punctal plug, the investigator will assess the removal characteristics of the plug.

NOTE: After the last study subject has had their punctal plug removed, the investigator will give an overall assessment on the removal characteristics of all punctal plugs that were inserted during the study.

An exit form will be completed at the final study examination (Visit 3), or whenever the study subject completes or leaves the study for any reason.

Schedule of Assessments, Events

EXAM PARAMETERS	v1	v2	v3
Inform Consent/HIPAA	①		
Demographic Data/Medical Hx	① A		
Subject Reports of any Ocular Signs or Symptoms	① B		
Verify No Ocular Drop use One Hour Prior to Visit	①	②	③
Inv. Evaluation of Subject's Acceptance of Study Plug			③ C
Slit Lamp Examination	① B	②	③ C
Tear Lake Evaluation	① B	②	③ C
Size Evaluation of Lower Puncta, Prior to Dilation	① B		
Dilation of Lower Puncta	①		
Insertion of a Punctal Plug	①		
Inspection of the Placement of the Punctal Plug	① D	②	③ C
Investigator Device Assessment of Insertion	① E		
Removal of Punctal Plug			③
Investigator Device Assessment of Removal			③ F
Adverse Device Event Recording	①	②	③

Keys to Abbreviations:

- A = Record medical history for the past 7 days
- B = PRIOR to **INSERTION** of punctal plug
- C = PRIOR to **REMOVAL** of punctal plug
- D = Slit-Lamp Evaluation of Punctal Plug **AFTER INSERTION**
- E = After EACH Study Subject and after **ALL** Study Subjects have had their Punctal Plug Inserted
- F = After EACH Study Subject and after **ALL** Study Subjects have had their Punctal Plug Removed

Visit Schedule:

- v1 = Screening/Baseline
- v2 = 7 ± 1 days post plug insertion
- v3 = 28 ± 4 days post plug insertion

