10.4.4 Safety Analyses

All study subjects who were inserted with a punctal plug will be evaluable for safety analysis. The safety endpoints in this study are clinically significant slit lamp biomicroscopy findings (lid, conjunctiva, and cornea), incident rate of plug extrusions, and the frequency and severity of any reported adverse device events. Safety variables will be summarized using descriptive statistics.

The type, severity, duration and frequency of reported adverse device events will be tabulated by visit. Additionally, any adverse device event experienced by a subject after signing informed consent and before exposure will be presented separately in the safety analysis.

Adverse device events will be coded using the Medical Dictionary for Regulatory Activities (MedDRA). Treatment emergent ADEs (those occurring after insertion of a study punctal plug) will be summarized descriptively: The number and percentage of study subjects who experienced an ADE and the total number of ADEs will be summarized by system organ class and preferred term. Associated ADEs, defined as ADEs suspected to be treatment related by the investigator, SADEs and serious associated ADEs will also be summarized, if necessary. Summaries of each type of event will be prepared by severity and for all severities combined.

Concomitant medication recorded and used during the study will be coded using the World Health Organization Drug Dictionary and listed by subject. Ocular concomitant medications will be identified by each eye in the listing.

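### The structured slit-lamp safety record has no item for the punctum, no scheduled examination after plug removal, and no required later examination of a first eye dilated without insertion

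*Combined protocol and SAP*

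**What the plan says.** **Structures.** Section 7.2.1(d) states that "Slit-lamp examination will include assessment of the lid, conjunctiva and cornea as normal or abnormal"; an abnormal finding is then marked as clinically significant or not, and described if it is. Section 10.4.4 carries the same list into the analysis: "clinically significant slit lamp biomicroscopy findings (lid, conjunctiva, and cornea), incident rate of plug extrusions". The endpoint in 4.2.3 has no anatomical limit: "Safety assessments will include any clinically significant slit-lamp biomicroscopy findings, any extrusions of a punctal plug, and incidence and severity".

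**Risks.** Among the less common but serious effects, 2.3 names "pyogenic granuloma, damage to the muscle at the opening of the punctum, canaliculitis, or migration of the plug into the canalicula".

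**Timing.** The Visit 1 examination is of the planned study eye, before sizing and dilation (synopsis and 7.3.1). Visit 2 has "Slit-lamp examination of the study eye" (7.3.3(b)). Visit 3 has "Slit-lamp examination, prior to the removal of the punctal plug" (7.3.4(c)). Early exit repeats the Visit 3 step, on condition that the plug has not been extruded (7.3.5(c)). Unscheduled safety visits are optional but include a slit-lamp examination (7.3.6).

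**Eyes.** The Note under 7.3.2 lets the investigator turn to the fellow eye "if the investigator is unable to insert the plug in the first eye chosen". If both eyes fail after dilation, the subject is discontinued and replaced (6.5.1). Section 10.4.4 limits the safety analysis to subjects in whom a plug was inserted.

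**The concern.** Dilation, plug wear and removal all act on the punctum. The one structured tissue examination in the safety plan has no entry for it, stops before the final procedure, and follows only the eye that ends up with the plug.

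What is at stake is what the slit-lamp table can support. A report of no clinically significant slit-lamp findings could be read as covering the site where the device sits. On the protocol text it would cover lid, conjunctiva and cornea, with the plug still in place at the last examination. With at most 40 eyes, any statement about absent harm is already weak. It is weaker still for findings that have no field to be entered in.

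**Working it through.** The plan gives no figure on this point, so the check is a comparison of sections, followed by one piece of arithmetic for context.

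**1. Structure.** The list in 7.2.1(d) and the list in 10.4.4 agree: lid, conjunctiva, cornea. Some risks in 2.3 fit that list, such as subconjunctival hemorrhage and surface inflammation. Damage to the punctal muscle, canaliculitis and migration are located by their own wording at the punctum or canaliculus, for which there is no item. The analysis in 10.4.4 is thus narrower than the endpoint in 4.2.3.

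**2. Timing.** Scheduled slit-lamp examinations are at Visit 1 before sizing and dilation, at Visit 2 with the plug in place, and at Visit 3 or early exit before removal. The steps listed after removal are ADE recording and the assessment of removal characteristics; neither is a slit-lamp examination. Section 6.4 itself warns that the cap can tear and the plug can fracture or intrude. An early exit after extrusion has no slit-lamp step in 7.3.5. Section 5.5.1.1 asks for an end-of-study safety evaluation of terminated subjects but does not say what it contains.

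**3. Eyes.** The first eye chosen was the planned study eye, so it has a baseline examination. After a failed attempt and a switch, Visit 2 names the study eye and Visit 3 names no eye. Nothing requires the attempted eye to be examined again. If both eyes fail, the subject is replaced and falls outside the safety population.

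**4. Other routes for a punctal finding.**
- Plug inspection at Visits 1, 2 and 3. Section 6.2(h) has the punctal opening viewed after insertion, for the stated purpose of confirming retention and placement. No tissue record is described.
- ADE reporting (8.1), by investigator observation, spontaneous report or one standard question. It gives no denominator of puncta examined.
- Technical complaints (6.4, 8.6.2) for a torn or separated plug, including whether an ADE was associated.
- For an attempted eye, the rules differ. Section 8.1 restricts ADE recording to events during or after insertion, 8.5 starts at Visit 1, and 10.4.4 presents events between consent and exposure separately.

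**5. Context on size.** With n = 40 eyes (4.2) and zero events, the exact one-sided 95% upper bound is 1 − 0.05^(1/40) = 7.2%. The two-sided Clopper-Pearson limit is 1 − 0.025^(1/40) = 8.8%. The chance of at least one event, 1 − (1 − p)^40, is 33%, 55% and 87% for assumed true rates p of 1%, 2% and 5%. All of these presume that an event, if present, is recorded. If the slit-lamp table records only a fraction s of punctal harms, the one-sided bound on the harm rate becomes 7.2%/s: 14.4% at s = 0.5 and 28.9% at s = 0.25. The value of s is unknown, so these are illustrations and not estimates.

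**The case against.** The strongest reply is that the plan already watches the plug site. It is viewed at the slit lamp at all three visits, and 4.2.3 and 8.1 cover any clinically significant slit-lamp finding. The plug cap sits at the lid margin, so an investigator may enter a punctal finding under lid. Migrations are expressly reportable as ADEs, superficial ones excepted, and other punctal harms can enter as investigator-observed ADEs, a safety endpoint listed alongside. ADE recording follows removal at Visit 3, torn plugs are technical complaints, and events between consent and exposure are presented separately. This is a small uncontrolled pilot with descriptive safety summaries.

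Much of this stands. A reader might infer that the protocol never looks at the punctum or that harm there would be lost. The documents do not support that, because several routes exist and the Visit 1 and unscheduled examinations add to them. What remains is that none of these routes is a structured tissue record with a known denominator. Reading lid to include the punctum would depend on the site, and would not supply an examination after removal or of the attempted eye.

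**Conclusion.** The concern holds in a limited form. The structured slit-lamp endpoint does not systematically record punctal findings, has no scheduled examination after removal, and requires no later examination of a first eye dilated without insertion. A clean slit-lamp table would not by itself show that the punctum was unharmed. The timing gap applies to every planned removal, up to 40. The number of attempted eyes cannot be derived from the documents. Importance is optional to modest.

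Three stronger inferences are not supported:
- That the safety results are biased toward a clean outcome. Incomplete structured ascertainment is a limitation; bias is not shown, since ADEs are an equal safety endpoint and no section ranks slit-lamp findings above the others.
- That attempted eyes are those with the most difficult dilations. Section 6.2 notes that the punctum may also constrict before the plug can be inserted.
- That the punctum goes unrecorded in practice. The CRF is not in the documents, and its plug-inspection or removal pages may hold such a field.

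The conclusion rests on the protocol text alone.

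**What to change.** - In 7.2.1(d) and 10.4.4, add punctum as a fourth normal/abnormal item, with clinical significance, at each existing slit-lamp examination, including baseline.
- Record that item once more directly after removal at Visit 3 and at early exit, and summarise pre- and post-removal findings separately. State what is recorded at early exit when the plug has extruded, so that 7.3.5 and 5.5.1.1 agree.
- For any eye dilated without insertion, record the item at Visit 1 after the failed attempt. This also reaches subjects in whom both eyes fail, who have no Visit 2. Record it again at Visit 2 if the subject continues with the fellow eye. List these eyes separately, because the safety population in 10.4.4 contains inserted subjects only.
- Reconcile 8.1, 8.5 and 10.4.4 on events that occur before insertion.

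The cost is a few extra CRF entries, about a minute at a slit lamp already in use, an added summary and listing, and somewhat more recorded findings. No new visit or instrument is needed. Under 7.1 the change would go through a protocol amendment with IRB approval. A punctum item will not show a plug that has moved deep into the canaliculus; that still depends on plug inspection and ADE reporting.

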7.3 Study Visit Schedule

7.3.1 Visit 1: Day 0 - Screening (Prior to punctal plug insertion)

A potential study subject qualifications will be assessed according to the inclusion/exclusion criteria listed in the protocol (see Sections 5.2 and 5.3). Prior to undergoing any study-specific procedures, both the study Informed Consent and Authorization for Use/Disclosure of Health Information forms (HIPAA authorization) must be signed by a potential subject who has agreed to participate in the study. During this visit, the following information will be collected/evaluated and recorded in the appropriate sections of the study case report forms of a subject, prior to the sizing and dilation of the lower punctum for the planned study eye.

- a. Obtain informed consent and HIPAA authorization release
- b. Record the subject's demographic data and prior 7 days medical history
- c. Verify a subject has not used any ocular drops within the last hour prior to their baseline visit
- d. Record any subject reports of ocular signs or symptoms they are currently experiencing
- e. Slit-lamp examination of the planned study eye

7.3.2 Visit 1:Baseline - Day 0 (Insertion of a punctal plug - refer to Section 6.2 for details regarding the insertion of the NDE punctal plug)

After the screening examination, a qualified study subject will be sequentially assigned an ID number. In addition, the ID number and the study subject initials will be recorded on study case report forms, in lieu of recording his/her name, in order to maintain subject confidentiality.

Note: The investigator has the option of inserting the plug in either the left or right eye of the subject. However, if the investigator is unable to insert the plug in the first eye chosen, the investigator can insert the plug in the fellow eye as long as the fellow eye meets all study inclusion/exclusion criteria.

- f. Tear lake evaluation of the planned study eye prior to the sizing and dilation of the lower punctum
- g. Size evaluation of the punctum of the planned study eye prior to the dilation of the lower punctum
- h. After dilation, the study punctal plug is inserted in to the lower punctum of study eye, inspect the punctal plug using the slit-lamp, the position of a study punctal plug may be adjusted with forceps.
- i. Record any reported adverse device event(s)

j. After the study plug has been inserted in the lower puncta, the investigator will assess the insertion characteristics of the plug.

NOTE: After the last study subject has been inserted with a study punctal plug, based on all subjects enrolled in the study, the investigator will give an overall assessment on the insertion characteristics of the study punctal plug.

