5.3 Study Subject Exclusion Criteria

The following are exclusion criteria for potential study subjects' wishing to participate in this study:

- a. A subject with a history of complications, adverse events, trauma or disease in the nasolacrimal area, whether or not it was due to punctal plug wear, including but not limited to dacryocystitis, inflammation or canaliculitis in either eye
- b. A subject with a history of intolerance to punctal plugs
- c. A subject with structural lid abnormalities (e.g., ectropion, entropion) in either eye
- d. A subject with any clinically significant lid, conjunctival or corneal findings in either eye at the baseline visit
- e. A subject with a puncta >0.9 mm prior to dilation in either eye
- f. A subject with a severe dry eye condition
- g. A subject experiencing epiphora in either eye
- h. A subject experiencing any clinically significant ocular pain or discomfort in or around either eye at the baseline visit
- i. A subject with a known sensitivity to any inactive ingredient of the punctal plug, silicone, topical anesthetic, or any other products required for the study
- j. A subject currently participating or has participated in another clinical trial within 30 days prior to enrollment.

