10.4.2 Analysis of the Primary Endpoint(s)

The primary study variable will be based on the change from baseline in tear lake values. For analyses, using the intent-to-treat (ITT) data set, all data from all subjects with at least one follow-up evaluation of the tear lake will be evaluated. For the per protocol (PP) analyses dataset, data from subjects or visits with significant protocol deviations will be excluded.

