10.4.3 Analysis of the Secondary Endpoint(s)

Secondary endpoints will be based on changes from baseline in the severity of epiphora. For the investigator's evaluation of the subject's acceptance of the punctal plug, data from all subjects will be evaluated. Investigator evaluation of insertion and removal characteristics will be tabulated by study subject and overall evaluation. For analyses using the intent-to-treat (ITT) data set, all data from all subjects with at least one assessment of epiphora, subject acceptability and punctal plug characteristics evaluations will be included. For the per protocol (PP) analyses dataset, data from subjects or visits with significant protocol deviations will be excluded.

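### The study eye is chosen by the unmasked investigator with no rule and no requirement to fix the choice before looking, which can bias the uncontrolled tear lake change and, by a separate route, flatter the insertion ratings

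*Combined protocol and SAP*

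**What the plan says.** The note in Section 7.3.2, repeated under Study Design in the synopsis, reads: "The investigator has the option of inserting the plug in either the left or right eye of the subject". It then allows a second choice: "if the investigator is unable to insert the plug in the first eye chosen, the investigator can insert the plug in the fellow eye", provided the fellow eye is eligible. No default eye, random assignment or worse-eye rule is given, and no record of the reason is asked for.

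The Visit 1 procedures refer to an eye already named. Section 7.3.1 lists "Slit-lamp examination of the planned study eye" and Section 7.3.2 lists "Tear lake evaluation of the planned study eye prior to the sizing and dilation of the lower punctum". Follow-up covers the same eye only; Section 7.3.3 lists "Tear lake evaluation of the study eye". The study is open-label with one arm (Section 4.1), and Section 10.4.2 makes the primary variable "based on the change from baseline in tear lake values".

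On insertion, Section 10.4.3 says: "Investigator evaluation of insertion and removal characteristics will be tabulated", by subject and overall. Section 7.3.2 places the rating after the plug is in. Under Sections 5.5.1.2 and 6.5.1, a subject in whom neither eye can be inserted is discontinued and replaced.

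Section 5.3 applies several exclusions to both eyes, for example "A subject with a puncta >0.9 mm prior to dilation in either eye". The synopsis limits the same criteria to the planned study eye.

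**The concern.** Two mechanisms are possible, and they act on different endpoints.

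The first concerns the tear lake. Part of any difference between a subject's two eyes on a given day is temporary. If the investigator takes the eye that looks drier, the temporary part is on average low in that eye at baseline and has gone by Day 7 or Day 28. The mean change is then positive even if the plug does nothing. With no control arm and no fellow-eye readings, the planned analysis can neither detect nor remove this.

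The second concerns insertion. Taking the easier punctum, moving to the other eye after a failure, rating only completed insertions and replacing double failures all remove difficult insertions from the ratings. Ease of insertion need not be related to tear height, so this does not by itself produce regression to the mean.

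**Working it through.** The plan gives no effect size, SD or power, so there is no figure of its own to reproduce. From the documents: up to 40 subjects, one eye each (Section 4.2); two-sided 5% tests (Section 10.4.1); one baseline reading in the chosen eye. Everything else is assumed. That includes the paired t-test, since Section 10.4.2 names no test.

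**Can the choice depend on appearance?** The recorded reading is taken in an eye already planned, so random error in that reading should not drive the choice. But the investigator may look at both eyes first. The either-eye exclusions in Section 5.3 in fact require both to be assessed, and nothing requires the choice to be written down before that look. The nearest model is therefore selection on a separate, unrecorded look on the same day.

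**Model for the tear lake.** Set the variance of one eye's reading within a subject to 1. A share f is transient and 1 − f is a persistent eye difference. Assume half of the transient variance (f/2) is real same-day fluctuation and half (f/2) is reading error. The look shares the fluctuation but has its own error of the same size. There is no plug effect.

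- Expected value of the lower of two independent standard normal looks: −1/√π = −0.564.
- Part of that due to same-day fluctuation: −0.564 × f/2. It does not carry over to follow-up, so the bias is +0.282f.
- SD of change: √(2f).
- Standardised bias if the drier-looking eye is always chosen: 0.282f/√(2f). The rejection rate follows from the noncentral t with 39 degrees of freedom and noncentrality equal to the standardised bias × √40.

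| Transient share f | Choices following appearance | Bias (SD of change) | Two-sided rejection, no plug effect |
|---|---|---|---|
| 0.25 | all | 0.0705/0.707 = 0.10 | 9% |
| 1 | all | 0.282/1.414 = 0.20 | 23–24% |
| 0.25 | a quarter | 0.10/4 = 0.025 | 5% |
| 1 | a quarter | 0.20/4 = 0.05 | 6% |
| any | none (random, or on a stable difference) | 0 | 5% |

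Simulation (20,000 trials per setting) agrees with these values. For scale, the standardised change detectable with 80% power at 40 subjects is (1.960 + 0.842)/√40 = 0.44.

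**Shared variation.** If both eyes also rise and fall together between visits, with variance f (assumed), the SD of change becomes √(4f). The always-drier case falls to 0.10/√2 = 0.07 and 0.20/√2 = 0.14 SD, with rejection of 7% to 14%.

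**Insertion.** Let p be the first-eye failure rate and ρ the correlation of failure between eyes. The share of subjects counted as inserted despite a failed first eye is p − [p² + ρp(1 − p)]. With p = 10%:

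- ρ = 0: 0.10 − 0.01 = 9%.
- ρ = 0.5: 0.10 − (0.01 + 0.045) = 4.5%.

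With p = 5% the range is 2.4% to 4.8%, and with p = 20% it is 8% to 16%. The documents give no failure rate.

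**The case against.** The best defence is the order of procedures. The reading is listed for a planned eye, so the choice nominally comes first. The documents give no sign that investigators would prefer the drier eye. Section 5.1 describes healthy volunteers, severe dry eye is excluded, and Section 2.3 offers participants no treatment benefit. If the eye is chosen for convenience, subject preference or a lasting difference, the tear lake bias is zero. This is also a pilot with no sample-size calculation (Section 10.5).

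Most of this stands as a limit on size. It does not remove the possibility, because nothing fixes the choice before the look. Nor does the pilot label dispose of it, since Section 10.2.1 states formal hypotheses tested at 5%.

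A reader might infer much larger effects. Choosing the lower eye on the very reading recorded as baseline gives 0.564f/√(2f), that is 0.20 to 0.40 SD and 23% to 69% rejection for f from 0.25 to 1. The documents do not support that model, because they take the recorded reading in one eye already named. A reader might also say the bias favours the study's hypothesis. Section 10.2.1 is non-directional; a rise is only what the occlusion mechanism in Section 2.1 would lead one to expect.

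On insertion, the ratings are tabulated with no hypothesis attached. The overall assessment is meant to reflect all enrolled subjects, and double failures are documented as discontinuations. So those failures are not wholly lost, but no rating or tabulation of a failed first eye is described.

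**Conclusion.** The concern holds as a gap in design, not as evidence that the result will be wrong. The eye is chosen without a rule by an unmasked investigator, and the primary analysis cannot separate a selection artefact from a plug effect. Under the stated variance assumptions, the tear lake bias is about 0.10 to 0.20 SD of change (9% to 24% rejection) if every choice follows same-day appearance, and about 0.03 to 0.05 SD (5% to 6%) if a quarter do. It is less if visit-to-visit variation is shared between eyes, and nil if the choice is unrelated to the eye's state that day. How often investigators would choose on appearance is unknown.

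The insertion part is firmer, because it follows from the written rules on switching, timing of the rating and replacement. Its size depends on a failure rate that the documents do not give. The point is worth correcting because it is cheap and cannot be repaired in the analysis.

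**What to change.** 1. At consent, before any eye examination, assign left or right from a pre-printed random list keyed to consent or screening order. It cannot be keyed to the subject ID, which Sections 7.3.2 and 10.5.1 assign only after screening.
2. Use the fellow eye only if the assigned eye is ineligible or cannot be inserted, and record the reason on the CRF.
3. Tabulate first-attempt insertion success over all attempted eyes, including failed first eyes and subjects later replaced. The list alone does not cure the insertion ratings, because the switch remains.
4. Reconcile the eye scope of the exclusion criteria between the synopsis and Section 5.3. Until that is done, it is unclear when an ineligible assigned eye leads to use of the fellow eye and when it excludes the subject.

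The cost is a short list to administer, a CRF field or two, one extra table and the loss of investigator discretion over the eye. No visits or procedures are added.
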